4.2. Measures Taken to Avoid Bias

This is an open-label study; no formal comparisons will be made between subjects or against historical controls. Measurements of safety and efficacy are objective measurements, and only comparisons to pretreatment conditions will be made.

4.3. Number of Subjects

4.3.1. Planned Number of Subjects

Up to approximately 163 subjects may be enrolled in the study:

- Part 1 Dose Escalation – Approximately 18 to 42 evaluable subjects.
- Part 1 Safety Expansion – Approximately 18 to 36 evaluable subjects.
- Part 2 – Up to 85 evaluable subjects (up to 45 in Stage 1 and up to 40 in Stage 2).

4.3.2. Replacement of Subjects

Subjects may be replaced for any of the following reasons:

- Subject is not evaluable for DLTs (see [Section 5.4.2](#)).
- In Part 1 Safety Expansion and Part 2, subject has not met the biopsy requirements for the study (ie, pre- and on-treatment samples).
- Subject does not meet the eligibility requirements of the study (eg, accidental enrollment).

4.4. Duration of Treatment and Subject Participation

After signing the ICF, screening assessments may be completed over a period of up to 28 days. Each subject enrolled in the study may continue to receive INCAGN01949 as long as the subject is deriving benefit and has not met any of the Protocol-defined conditions for treatment withdrawal (see [Section 5.5](#)). If the subject discontinues treatment with INCAGN01949, then the treatment period will end, and the subject will enter the follow-up period (see [Section 6.4](#)). Subjects are expected to participate in the study for a maximum of 14 months.

4.5. Overall Study Duration

The study begins when the first subject signs the ICF. The end of the study will occur when all subjects have completed the last study follow-up visit or have discontinued study drug and have completed applicable follow-up assessments.

4.6. Study Termination

The investigator retains the right to terminate study participation at any time, according to the terms specified in the study contract. The investigator is to notify the institutional review board (IRB)/independent ethics committee (IEC) in writing of the study's completion or early termination, send a copy of the notification to the sponsor or sponsor's designee, and retain 1 copy for the site study regulatory file.

The sponsor may terminate the study electively, if required by regulatory decision, or upon review of emerging data. If the study is terminated prematurely, then the sponsor or designee will notify the investigators, the IRBs and IECs, and regulatory bodies of the decision and reason for termination of the study.

5. TREATMENT

5.1. Treatment Assignment

5.1.1. Subject Numbering and Treatment Assignment

All subject numbers will be 6 digits; the first 3 digits will be the site number, and the last 3 digits will be the subject's number. This subject number will be maintained throughout the study and will not be reassigned. Subjects who withdraw consent or discontinue from the study after being assigned a subject number will retain their number.

This is a nonrandomized study, in which subjects will be enrolled into either Part 1 or Part 2 as described previously, with all subjects receiving INCAGN01949 (herein referred to as study drug). Site staff will contact the interactive response technology (IRT) at the time of screening, when enrolling subjects, and when ordering study drug for all treatment cycles, as well as to discontinue subjects from treatment. Refer to the IRT manual for detailed information.

5.1.2. Randomization and Blinding

This is an open-label nonrandomized study; therefore, randomization and blinding do not apply.

5.2. INCAGN01949

5.2.1. Description and Administration

The study drug (INCAGN01949) is in liquid form in the formulation buffer of 20 mM histidine, 250 mM sorbitol, pH 6.5 at a strength of 10 mg/mL to be used for IV infusion. The infusion site should not be used for blood sampling.

Study drug will be diluted in 0.9% normal saline or acceptable admixture as outlined in the Pharmacy Manual and will be administered by qualified personnel as an IV infusion over 30 minutes (-5/+10 minutes) on Day 1 of each cycle. In Part 1, subjects will be administered study drug, according to cohort enrollment ([Table 2](#)). In Part 2, subjects will be administered study drug at the recommended dose and schedule. Subjects will continue to receive INCAGN01949 as long as the subject is deriving benefit and has not met any of the Protocol-defined conditions for treatment withdrawal (see [Section 5.5](#)).

The Pharmacy Manual contains additional information and instructions for study drug preparation and infusion.

5.2.2. Supply, Packaging, and Labeling

Study drug will be supplied as 5 mL of aqueous solution in 10 mL glass vials with 10 mg/mL of INCAGN01949. Study drug will be packaged as open-labeled supplies, and each vial will be labeled and placed in protective packaging. The Pharmacy Manual contains additional information regarding supply, packaging, and labeling of study drug.

The investigator will take responsibility for and take all steps to maintain appropriate records and ensure appropriate supply, storage, handling, distribution, and usage of study drug in accordance with the Protocol and any applicable laws and regulations.

All Incyte investigational product labels will be in the local language and will comply with the legal requirements of each country.

5.2.3. Storage

Study drug must be stored refrigerated (2°C-8°C) and protected from light in a secure, limited-access location. Receipt and dispensing of study drug must be recorded by an authorized person at the study site. Study drug may not be used for any purpose other than that stated in the Protocol. The Pharmacy Manual contains additional information regarding storage of study drug.

5.3. Treatment Compliance

INCAGN01949 is administered as an IV infusion by site personnel. Receipt of infusions will be documented by the site staff and monitored by the sponsor/designee.

5.4. Treatment Interruptions and Adjustments

5.4.1. Dose Modifications

Selections and modifications to the study drug regimen are planned for dose-escalation cohorts. Dose interruptions and modifications also may occur for individual study subjects. The identification of DLTs will define the doses used in planned cohorts (see [Section 5.4.2](#)). Further, the occurrence of DLTs and other toxicities (related or unrelated to study drug) will guide decisions for treatment interruptions and discontinuation for individual subjects.

Intrasubject dose escalation is not permitted; however, once the recommended dose has been determined, ongoing subjects in Part 1 may be permitted to dose escalate to the recommended dose and schedule with approval of the medical monitor.

5.4.2. Dose-Limiting Toxicity and Determination of Maximum Tolerated Dose

The evaluation period for DLTs will begin on Cycle 1 Day 1 and will continue up to and including study Day 28. All DLTs will be assessed by the investigator using CTCAE v4.03. A DLT will be defined as the occurrence of any toxicity in [Table 3](#), with the exception of events clearly associated with the underlying disease, disease progression, a concomitant medication, or comorbidity.

Individual subject dose reductions may be made based on events observed at any time during treatment with study drug; however, for the purposes of dose cohort escalation/de-escalation, expanding a dose cohort, and determining the MTD/PAD of study drug, decisions will be made based on events that are observed from the first day of study drug administration through and including study Day 28. A lower MTD may subsequently be determined based on relevant toxicities that become evident after Day 28.

Table 3: Definition of Dose-Limiting Toxicity

Nonhematologic toxicity

 • Any \geq Grade 3 nonhematologic toxicity EXCEPT the following: 
 – Transient (\leq 72 hours) abnormal laboratory values without associated clinically significant signs or symptoms. – Nausea, vomiting, and diarrhea adequately controlled with supportive care within 48 hours. – Changes in cholesterol and triglycerides. – An event clearly associated with the underlying disease, disease progression, a concomitant medication, or comorbidity. – Asymptomatic changes in lipid profiles. – Asymptomatic changes in amylase and lipase. – Singular or nonfasting elevations in blood glucose (ie, blood glucose excursions will be considered toxicities if fasting blood glucose is elevated on 2 separate occasions).
Hematologic toxicity

 • Grade 3 thrombocytopenia with clinically significant bleeding (ie, requires hospitalization, transfusion of blood products, or other urgent medical intervention). • Grade 4 thrombocytopenia. • \geq Grade 3 febrile neutropenia (absolute neutrophil count $< 1.0 \times 10^9/L$ and fever $> 101^\circ F/38.3^\circ C$). • Grade 4 neutropenia that does not recover to \leq Grade 2 in ≤ 3 days after interrupting study drug. • Grade 4 anemia not explained by underlying disease or some other concomitant disorder.
Immune-related toxicity^a

 • \geq Grade 2 ocular irAEs will be considered a DLT. • Grade 3 irAEs that do not improve to baseline or at least Grade 1 in < 5 days with appropriate care or with corticosteroid therapy will be considered a DLT. • Grade 4 irAEs will be considered a DLT regardless of duration.
General

 • Inability to receive the planned number of doses within the 28-day DLT period due to toxicity, regardless of grade, will be considered a DLT.
MTD

 • In Part 1 of the study, the MTD will be defined as 1 dose level below that at which \geq one-third of subjects in a particular cohort have DLTs. • In Part 2 of the study, toxicities will continue to be monitored. If the cumulative incidence of DLTs occurs in $\geq 33\%$ of subjects after 6 subjects have been observed for at least 28 days, further enrollment may be interrupted, and the investigators and sponsor will meet and reassess the MTD. All AEs, regardless of the time of occurrence on study, may be considered in DLT determination purposes.
MNTD

 • For each dose and schedule explored, if $> 33\%$ of subjects (minimum of 6 subjects) experience a \geq Grade 3 toxicity related to study drug after completing ≥ 4 cycles, then treatment will be stopped, and the MNTDs will be determined in conjunction with the investigators and sponsor based on all available safety data. All AEs, regardless of the time of occurrence on study, may be considered in DLT determination decisions.

Note: Transient (≤ 72 hours) abnormal laboratory values without associated clinically significant signs or symptoms based on investigator determination will not be considered DLTs.

^a Immune-related AEs are a diagnosis of exclusion, after alternative etiologies have been ruled out.

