Reference Therapy, Dosage, and Mode of Administration:

Not applicable.

Study Schedule/Procedures:

Subjects will have regularly scheduled study visits at the clinical site on Day 1 of each cycle. Additional study visits may be required during some cycles to monitor for safety, efficacy, or for PK/■ evaluations. Study visits are as follows:

- **Screening:** up to 28 days before enrollment. Screening will begin at the time that the subject signs the informed consent and will continue until the date that the subject is enrolled in the study (Cycle 1 Day 1).
- **Cycle 1:** Day 1, Day 2, and Day 7 (± 1 day).
- **Cycle 2:** Day 1 (± 1 days) and Day 7 (± 1 day).
- **Cycle 6:** Day 1 (± 3 days), Day 2, and Day 7 (± 1 day).
- **All other treatment cycles:** Day 1 (± 3 days).
- **Efficacy assessments:** Every 8 weeks (± 7 days) for 12 months, and every 12 weeks (± 7 days) thereafter until disease progression is determined.

- **End of treatment:** \pm 3 days of withdrawal from study.
- **Safety follow-up:** 30 days (+ 7 days) and 60 days (+ 7 days) after end of treatment.

Safety Assessments:

Subjects will have regularly scheduled study visits at the clinical site on Day 1 of every cycle where targeted physical examinations, vital sign collection, ECOG performance status, collection of concomitant medications, and AE assessments will be performed. A 12-lead ECG will be performed at screening, Cycle 1 Day 1, Cycle 2 Day 1, and then Day 1 of **every other cycle** after Cycle 2 (eg, Cycle 4, Cycle 6, Cycle 8). Triplicate ECG measurements will be performed at screening, Cycle 1 Day 1, and Cycle 6 Day 1, in conjunction with PK assessments. Laboratory assessments will be collected on Day 1 of each cycle, with more frequent blood sample collection during the first and second cycles (Day 1 and Day 7) to evaluate for DLTs. Toxicities will be monitored continuously and will be graded using the NCI CTCAE v4.03 criteria.

On Day 1 of the first 4 cycles (Cycle 1 Day 1, Cycle 2 Day 1, Cycle 3 Day 1, and Cycle 4 Day 1), subjects will be required to stay at the study site for at least 4 hours after infusion of study drug for safety observation. It is recommended that the subject does not leave the site for any reason during the safety observation period. During the safety observation period, subjects will be assessed for the onset of acute AEs.

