4. INVESTIGATIONAL PLAN

4.1. Overall Study Design

This is an open-label, nonrandomized, Phase 1/2 study to determine the safety and tolerability, define the MTD or PAD, and assess the preliminary efficacy of INCAGN01949 in subjects with advanced or metastatic solid tumors. Subjects will receive INCAGN01949 on Day 1 of each cycle. Part 1 of the study will begin with 14-day cycles; however, alternate dose administration schedules may also be explored depending on PK, [REDACTED], and safety results. The study will be conducted in 2 parts:

- Part 1 – Dose Escalation and Safety Expansion will determine the PAD, defined as a dose that provides a maximal biochemical effect [REDACTED], and/or the MTD of INCAGN01949, which includes defining the optimal dose administration schedule and the maximum number of tolerated doses (MNTD).
- Part 2 – Dose Expansion will evaluate the recommended dose and administration schedule determined in Part 1 in subjects with select tumor types [REDACTED] including adenocarcinoma of the endometrium, ovarian cancer, RCC, melanoma, and NSCLC.

See [Figure 2](#) for overall study design.

4.1.1. Part 1

In Part 1, subjects with advanced or metastatic solid tumors who progressed after treatment with available therapies that are known to confer clinical benefit, who are intolerant to treatment, or who refuse standard treatment will be enrolled.

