4.1.1.1. Dose Escalation

In the dose-escalation part of the study, a 3 + 3 design will be utilized to determine the MTD or PAD of INCAGN01949. A minimum of 3 evaluable subjects will be enrolled in each cohort beginning with Cohort 1 (7 mg; starting dose). There will be a waiting period of 48 hours between dose administration to the first subject and second subject of each dose cohort. The first 3 subjects enrolled within a cohort will be observed for a DLT observation period of 28 days before the next cohort begins enrollment. The dose will be escalated if 0 of the first 3 evaluable subjects enrolled has a DLT. If 1 of the first 3 evaluable subjects enrolled has a DLT, then the cohort will be expanded to include 3 additional evaluable subjects, and if no DLT occurs in the additional 3 subjects, then the dose will be escalated. If a DLT occurs in one-third or more of the expanded cohort, then the MTD will be deemed to be exceeded, and the previous dose level will be considered the MTD. If only 3 subjects were treated at the MTD or PAD, then a minimum of 3 additional subjects will be enrolled before this dose is administered in Part 2 of the study.

If Cohort 1 (7 mg; starting dose) exceeds the MTD, then the sponsor and investigators will consider administering INCAGN01949 at 2 mg (Cohort -1) and/or investigate 7 mg at alternate dose schedules (eg, every 3 week administration), based on available safety, PK, [REDACTED] data. If an alternate schedule is tested and determined to be safe, then re-escalation of INCAGN01949 will proceed according to [Table 2](#).

Throughout the treatment period, if > 33% of subjects (a minimum of 6 subjects) experience a Grade \geq 3 toxicity related to study drug after completing \geq 4 cycles, then dose administration will be stopped, and the MNTD will be determined in conjunction with the investigators and sponsor based on all available safety data.

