6. STUDY ASSESSMENTS

All study assessments will be performed as indicated in the schedule of assessments ([Table 7](#)), and all laboratory assessments will be performed as indicated in [Table 8](#) and [Table 9](#). [Table 10](#) presents a summary of clinical laboratory analytes to be assessed. The order of assessments is suggested by the order of mention within the schedule. See [Section 7](#) for instructions on each assessment. Further details of study procedures and assessments can be found in the study reference manual or applicable procedural documentation.

Table 7: Schedule of Assessments

Visit Day (Range)	Protocol Section	Screening	Treatment ^a				Post-Treatment ^b		
			C1 and C2		All Subsequent Cycles	Every 8 weeks	EOT	Safety Follow-Up Visit 1	Safety Follow-Up Visit 2
			D1	D7	D1	Disease Status			
Evaluation/Window		Day -28 to -1		± 1 day	± 3 days	± 7 days	± 3 days	30 days (+ 7 days)	60 days (+ 7 days)
Administrative procedures									
Informed consent	7.1	X							
Inclusion/exclusion criteria	3.1, 3.2	X	X						
Contact IRT	7.2	X	X		X		X		
Medical and cancer history	7.3	X							
Prior/concomitant medications	7.4	X	X	X	X		X	X	X
Administer INCAGN01949	5.2.1		X		X				
Poststudy anticancer therapy status	7.5							X	X
Clinical procedures/assessments									
Comprehensive physical examination including height	7.6.2.1	X							
Targeted physical assessment	7.6.2.2		X	X	X		X	X	X
Vital signs and weight	7.6.3	X	X ^c	X	X ^c		X	X	X
ECOG performance status	7.8	X	X	X	X		X	X	X
Laboratory assessments	7.6.5	X	X ^d	X	X		X	X	X
12-lead ECG ^e	7.6.4	X ^{f,g}	X ^g		X ^{g,h}		X	X	
AE assessment	7.6.1	X	X	X	X		X	X	X
Efficacy measurements									
Radiologic tumor assessments	7.7	X ⁱ				X ^j	X ^k		X ^k

^a Treatment cycles will begin every 14 days (± 3 days). Alternate dose schedules may also be explored based on emerging safety, PK, [REDACTED] data.

^b The mandatory safety follow-up visits should be conducted approximately 30 days and 60 days after the last dose of study drug or before the initiation of a new anticancer treatment, whichever comes first.

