7.6.5. Laboratory Assessments

A laboratory local to the study site and subject will perform all clinical laboratory assessments for safety (ie, blood chemistries, hematology assessments, coagulation tests, endocrine function, and urinalysis). The investigative site will enter the laboratory results and laboratory normal ranges into the eCRF. All local laboratory assessments should be performed using standard procedures on the days indicated in [Table 8](#). [Table 10](#) lists the specific laboratory analytes required for each test. Additional testing may be required by the sponsor based on emerging safety data. Additional tests may also be performed if clinically indicated.

Laboratory samples collected on study Day 1 must be performed before study drug administration. After Cycle 1, predose laboratory procedures can be conducted up to 72 hours before study drug administration (within the 3-day study window), and results should be reviewed by the investigator or qualified designee and found to be acceptable before a new cycle of treatment is initiated.

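### On 14-day cycles no safety visit or laboratory draw is required between about Day 22 and Day 28, so a silent laboratory DLT arising in that week may be first measured after the DLT window closes and need not be counted

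*Protocol*

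**What the plan says.** **The window.** Protocol 5.4.2: "The evaluation period for DLTs will begin on Cycle 1 Day 1 and will continue up to and including study Day 28". For escalation, cohort expansion and the MTD, the same section adds that "decisions will be made based on events that are observed from the first day of study drug administration through and including study Day 28". It then allows that "A lower MTD may subsequently be determined based on relevant toxicities that become evident after Day 28".

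**The cohort decision.** Protocol 4.1.1.1 says that the first three subjects "will be observed for a DLT observation period of 28 days before the next cohort begins enrollment". SAP 3.1.1 repeats this. Neither makes the decision wait for Cycle 3 Day 1 results.

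**The schedule.** Protocol 4.1: "Part 1 of the study will begin with 14-day cycles". The Safety Assessments part of the Synopsis plans "more frequent blood sample collection during the first and second cycles (Day 1 and Day 7) to evaluate for DLTs". Tables 7 and 8 put safety visits and laboratories on Day 1 and Day 7 of Cycles 1 and 2, and then on Day 1 of each later cycle with a window of 3 days either side. Protocol 7.6.5 adds that after Cycle 1 "predose laboratory procedures can be conducted up to 72 hours before study drug administration".

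**The concern.** A DLT window should end with a measurement, or at least not outlast the last one. Cycle 1 meets this standard: nothing is required in Days 8 to 14, but the Day 15 draw covers that stretch and falls inside the window. Cycle 2 has no equivalent, because the draw that would cover Days 22 to 28 is nominally on Day 29.

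The exposed events are qualifying laboratory toxicities without symptoms that last beyond 72 hours, such as Grade 4 thrombocytopenia or a persistent Grade 3 liver enzyme rise. If one arises in that week, it is a DLT at a site that draws the Cycle 3 sample on Day 27. It may not be one at a site that draws on Day 29.

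Two things are at stake. The DLT count behind the 3 + 3 rule and the fewer-than-3-of-9 expansion rule can be too low. The next dose level can also open before the covering results exist. This is a first-in-human escalation with no formal data monitoring committee (Protocol 8.7), so the count should not depend on when a site draws blood.

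**Working it through.** **1. Calendar.** With 14-day cycles, the study day of Cycle c Day d is 14(c − 1) + d.

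| Visit | Nominal study day | Allowed range |
|---|---|---|
| Cycle 1 Day 1 | 1 | – |
| Cycle 1 Day 7 | 7 | 6 to 8 |
| Cycle 2 Day 1 | 15 | 14 to 16 |
| Cycle 2 Day 7 | 21 | 20 to 22 |
| Cycle 3 Day 1 | 29 | 26 to 32 |

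The visit windows come from the Synopsis visit list and Table 7. The nominal gap is Days 22 to 28, which is 7 of 28 days (25%).

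**2. When the Cycle 3 laboratories can be drawn.** The 72-hour allowance gives:

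- dosing on Day 29: draw on Day 26 to 29;
- dosing on Day 31: draw on Day 28 to 31;
- dosing on Day 32: draw on Day 29 to 32, wholly outside the DLT window.

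A draw inside the window is therefore often possible, never required, and in the last case not available under the allowance.

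**3. Every-3-week schedule.** Cycle 2 Day 1 is Day 22 and Cycle 2 Day 7 is 22 + 6 = Day 28. There is no nominal gap; the problem belongs to 14-day cycles.

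**4. Reproducing the plan's operating characteristics.** Protocol Table 17 (SAP Table 2) follows from

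- 3 + 3 pass: (1 − p)³ + 3p(1 − p)² × (1 − p)³;
- both stages: that value × P(X ≤ 2), with X binomial (9, p).

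At p = 0.30: 0.343 + 3 × 0.30 × 0.49 × 0.343 = 0.494. With P(X ≤ 2) = 0.463, the joint value is 0.229. These match the stated 49.4% and 22.9%, and all six rows reproduce to rounding.

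**5. Illustration of size.** Let f be the share of DLTs detectable only by scheduled laboratories. Assume a constant hazard over 28 days and no Cycle 3 draw on Days 26 to 28. The counted rate is then 1 − (1 − p)^(1 − f × 7/28). At a true p of 30%:

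| f | Counted DLT rate | 3 + 3 pass | Pass both stages |
|---|---|---|---|
| 0 (as printed) | 30.0% | 49.4% | 22.9% |
| 25% | 28.4% | 52.7% | 26.6% |
| 50% | 26.8% | 56.1% | 30.9% |
| 100% | 23.5% | 63.3% | 40.7% |

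The documents give no value for f, so the table shows direction and range, not an estimate.

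**The case against.** The case for leaving the text alone has several parts.

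- **The draw can fall inside the window.** This stands. A reader might infer that such a DLT is always first measured on Day 29 and never counts. The documents do not support that, because a site drawing on Days 26 to 28 is fully on schedule. What fails is uniformity.
- **Toxicity after the second infusion is still tested.** This stands too. A reader might infer that laboratory follow-up stops 6 days after that infusion. It does not: the Cycle 3 predose draw tests it at about 14 days. The issue is whether the finding counts, not whether anyone looks.
- **Later toxicity can still be used.** Besides the sentence on a lower MTD, the MNTD row of Table 3 lets AEs at any time be considered in DLT determination. The sponsor and investigators also confer about weekly in Part 1 (8.7). But both sentences are permissive, neither enters the 3 + 3 or the 9-subject rule, and a call can review only results that exist.
- **Other monitoring fills the gap.** Weekly liver tests (Table 8, footnote b) start only after an abnormal result. Unscheduled visits (6.6) need a medical reason. Both help, and symptomatic events should be caught, but neither systematically detects a silent event that is new after Day 21. The missed-dose DLT in Table 3 does not help either: on nominal timing the doses in the window are those of Days 1 and 15.
- **The schedule is deliberate.** The Synopsis does name the Day 1 and Day 7 draws as the DLT laboratories. That explains the choice but does not cover a window running a week beyond the last of them.
- **The exposed class of events is narrow.** Table 3 excludes transient asymptomatic laboratory changes, lipids, and asymptomatic amylase and lipase changes, and it includes many clinical DLTs. This stands, and is why the 100% row is an extreme.

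**Conclusion.** The point holds in a limited form. On 14-day cycles no scheduled safety or laboratory assessment is required between about Day 22 and Day 28. Decisions rest on events observed through Day 28, and the next cohort need not wait for Cycle 3 Day 1. A non-transient, asymptomatic laboratory DLT arising in that week may therefore go uncounted, and whether it does depends on the timing of the site's draw.

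The effect can only lower the count, so it favours escalation. Its size cannot be fixed from the documents. The shift from 49.4% to between 52.7% and 63.3% at a true 30% rate rests on an undocumented laboratory-only share, a constant hazard, and no site drawing on Days 26 to 28. A reader might infer that Table 17 is wrong or that the DLT rate is understated by a known amount. Neither follows: Table 17 is correct for complete capture of DLTs, and how complete capture will be is unknown. This is a cheap improvement to the counting rule, not a demonstrated error in the design.

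**What to change.** Reconcile the DLT window and cohort-decision wording (Protocol 4.1.1.1 and 5.4.2, SAP 3.1.1) with the visit and laboratory schedule (Synopsis, Tables 7 and 8, Protocol 7.6.5), so that for 14-day cycles:

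1. an already scheduled safety laboratory assessment, the Cycle 3 Day 1 predose draw, closes the DLT window for every DLT-evaluable subject;
2. its results are in hand before the cohort decision;
3. the text states, uniformly for all sites, whether a qualifying finding first documented at that draw counts as a DLT;
4. the text states how subjects with a delayed or missed Cycle 3 Day 1 are handled.

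Schedules on which Cycle 2 Day 7 already falls on Day 28 should stay as they are. A blanket rule ending the window at Cycle 3 Day 1 would stretch it to Day 43 on an every-3-week schedule (22 + 21). Relying on the 72-hour allowance alone is also not enough, because dosing on Day 32 puts the earliest permitted draw on Day 29.

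The cost is wording, with no new visit or draw, and a wait of up to a few days per cohort.
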